6.4 Study Day 8 Visit (or Phone Call)

This visit will occur between study day 6-12. For those who were confirmed to have passed the pregnancy or had an aspiration procedure on Study Day 3, this visit will instead be a phone call to evaluate for bleeding or possible need for further evaluation.

- If this visit occurs in person, vital signs will be measured.

- Subjects who are scheduled to return for a visit on study day 8 will have a transvaginal ultrasound examination performed by a masked ultrasonographer. A pelvic exam will be performed if indicated.
- If no gestational sac is seen, the subject will receive contraception counseling and plan for a follow-up phone call on study day 30.
- If the examination demonstrates a persistent gestational sac, the options will be given for an aspiration procedure, a second dose of misoprostol or expectant management. The expectant management plan will include weekly visits for evaluation until the miscarriage is complete. These weekly visits will include a review of symptoms and adverse events, and an exam or ultrasound as indicated. They will also be offered active management if appropriate.
- Completed diary will be reviewed with subject. Adverse events will be reviewed and recorded.
- If subject requires additional visits, a new diary will be distributed.

6.5 30 Day Phone Call

All subjects will be contacted by telephone 30 days (range 25-36) after study day 1. Information on additional symptoms and treatment during the extended period will be recorded. Subjects will be asked to report any additional adverse events. The Post-Study Acceptability Questionnaire will be completed at this time, which will include the following scales: CES-D, Perceived Stress Scale, Adverse Child Experiences Questionnaire (ACE), and the Social Support Interview. The primary outcome of success (tissue expulsion after 1 dose of misoprostol with no additional need for medical/surgical intervention) or failure is ultimately confirmed at this 30-day point.

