6.2. Study Day 1 Visit

This visit may or may not occur on the same day as the screening visit.

Pre-Treatment

- If Study Day 1 does not occur on the same day as screening and there has been active vaginal bleeding since screening, the transvaginal ultrasound must be repeated.
- The subject will be questioned to obtain baseline information about her demographic characteristics and her medical, coital, menstrual, pregnancy, and contraceptive history. She will be given the following questionnaires to complete at home prior to inserting misoprostol and return at her next visit: CES-D and the Perceived Stress Scale.
- Rh-immune globulin 50 µg (“MICRhoGAM”) will be administered within 72 hours of this visit if the subject is Rh-negative and has not recently received Rh-immune globulin.
- Additional blood will be drawn (20 cc) and it will be stored for analysis of proteins and hormones.
- Vital signs, weight, and height (to calculate BMI) will be measured.
- A pelvic examination and/or Gonorrhea and Chlamydia testing may be performed if indicated
- The subject will be randomly assigned to one of the two study groups: 800µg (vaginally) misoprostol (group 1) or misoprostol 800 µg (vaginally) preceded by 200 mg mifepristone po (group 2). See Method for Assigning Subjects to Treatment Groups Section 3.1

Treatment

- If the participant is randomized to group 2, she will be given 200mg of mifepristone. She will swallow the tablet prior to being discharged from the study visit.

- All subjects will be given four 200 µg misoprostol tablets to place vaginally approximately 24 hours later at home.
- The subject will be offered prescriptions for pain relievers per local standards at each site.
- The participant will be instructed to abstain from sexual intercourse until the passage of the pregnancy has been confirmed.
- The subject will receive instructions about what to expect after misoprostol administration as per standard of care.
- A diary will be distributed to collect information about bleeding, pain medication use, and symptoms. The subject will be instructed on how to properly complete the diary. The subject should bring this diary to each visit.
- A follow-up appointment will be made for Day 3.

Treatment may be delayed per subject preference. If treatment is delayed, and there has been active vaginal bleeding since the last transvaginal ultrasound, the ultrasound must be repeated prior to dispensing drug.

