6.3 Study Day 3 Visit

This visit will occur between treatment day 3-6, ideally at least 24 hours after administration of misoprostol.

- Vital signs will be measured.
- A transvaginal ultrasound examination will be performed by a masked ultrasonographer. A pelvic exam will be performed if indicated.
- If the gestational sac is absent, the subject will need no further scheduled visits. She will receive a contraceptive prescription or device, if desired. She will receive a phone call on study day 8 to assess well-being.
- If the gestational sac is still present, the participant may opt for an aspiration procedure, a second dose of misoprostol or expectant management.
- If she opts for a second dose of misoprostol or expectant management she will be scheduled for an office visit on study day 8.
- If she has an aspiration procedure, no further visits are required and her study day 8 visit will instead be a phone call. She will receive a contraceptive prescription or device, if desired. If she chooses an aspiration procedure, but does not have the procedure prior to the day 8 time point, she will come to the office for the study day 8 visit for assessment.
- Approximately 20 cc of blood will be drawn and stored for analysis of possible biomarkers.
- Completed diary will be reviewed with subject. Adverse events will be reviewed and recorded.
- If subject requires a visit on study day 8, a new diary will be distributed.

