7.2. Statistical Methods

Primary Analysis: Baseline demographic characteristics of the subjects in the two groups will be examined. If the randomization is executed correctly, we expect no significant difference between the two groups on these variables. If there is an imbalance on certain variables (mostly likely by chance) and these variables also affect the outcomes variables, we will control for these variables using indirect standardization, Mantel-Haenzel stratified analysis or multivariable logistic (for categorical outcome) or linear regression (for continuous outcome). If there is a gross imbalance between the two groups, we will conduct in-depth evaluation to identify factors that may adversely affect randomization. Multivariable logistic and linear regressions will be used to adjust for the imbalance.

We will explore outcomes by clinical site; if there is no significant overall difference among the sites (homogeneous), we will pool sites together. However, if there is significant overall difference, we will identify which site(s) differ from others. Pairwise comparison will be conducted with Scheffe adjustment of significance level. In all following analyses, site will then be an independent variable for adjustment.

Both intent to treat and compliant populations will be analyzed. For categorical data, chi-square test will be used. For continuous variables, t-test will be used if the distribution is normal; otherwise rank-sum test or log transformation will be used. The following outcomes will be evaluated:

- Success rates between study arms for early pregnancy failure;
- Frequency of side effects and serious adverse events between study arms;
- Patient's satisfaction, anxiety, and acceptability of the treatment regimens;
- Cost analysis to compare these two treatments.

The outcome is defined as gestational sac expulsion with one treatment dose on Study Day 3 and no need for surgical intervention or medical intervention within 30 days of treatment. The overall success proportion, along with 95% confidence intervals, will be calculated for each treatment group. The

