The study period during which adverse events must be reported is normally defined as the period from the initiation of any study procedures to the end of the study treatment follow-up. For this study, the study treatment follow-up is defined as 30 days following the last administration of study treatment.

Post-study Adverse Event

All unresolved adverse events should be followed by the investigator until the events are resolved, the subject is lost to follow-up, or the adverse event is otherwise explained. At the last scheduled visit, the investigator should instruct each subject to report any subsequent event(s) that the subject, or the subject's personal physician, believes might reasonably be related to participation in this study. The investigator should notify the study sponsor of any death or adverse event occurring at any time after a subject has discontinued or terminated study participation that may reasonably be related to this study.

The sponsor should also be notified if the investigator should become aware of the development of cancer or of a congenital anomaly in a subsequently conceived offspring of a subject that has participated in this study.

Hospitalization, Prolonged Hospitalization or Surgery

Any adverse event that results in hospitalization or prolonged hospitalization should be documented and reported as a serious adverse event unless specifically instructed otherwise in this protocol. Any condition responsible for surgery should be documented as an adverse event if the condition meets the criteria for an adverse event.

Neither the condition, hospitalization, prolonged hospitalization, nor surgery are reported as an adverse event in the following circumstances:

- Hospitalization or prolonged hospitalization for diagnostic or elective surgical procedures for a preexisting condition. Surgery should **not** be reported as an outcome of an adverse event if the purpose of the surgery was elective or diagnostic and the outcome was uneventful.
- Hospitalization or prolonged hospitalization required to allow efficacy measurement for the study.
- Hospitalization or prolonged hospitalization for therapy of the target disease of the study, unless it is a worsening or increase in frequency of hospital admissions as judged by the clinical investigator.

9 Recording of Adverse Events

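### The call that confirms the primary outcome may be made 5 or 6 days before the outcome's own 30-day window closes

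*Combined protocol and SAP*

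**What the plan says.** The document sets several periods of about 30 days, and they start from different points.

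- Section 6.5 times the last scheduled contact from Study Day 1: "All subjects will be contacted by telephone 30 days (range 25-36) after study day 1". It adds that success or "failure is ultimately confirmed at this 30-day point".
- Section 7.2 counts a success as expulsion with one dose, seen on Study Day 3, and "no need for surgical intervention or medical intervention within 30 days of treatment".
- Section 3.1 places the last assessment 30 days after treatment. Sections 4.4.2 and 6.4 speak of study day 30.
- Section 8.1, on the adverse event reporting period, says that "the study treatment follow-up is defined as 30 days following the last administration of study treatment".

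On drug timing, Section 6.2 has group 2 swallow mifepristone at the Day 1 visit and gives every woman misoprostol tablets "to place vaginally approximately 24 hours later at home". It also says: "Treatment may be delayed per subject preference". No limit on the delay is stated.

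If the gestational sac persists, a second misoprostol dose is one of the options at the Day 3 visit ("This visit will occur between treatment day 3-6") and again at the Day 8 visit ("This visit will occur between study day 6-12").

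**The concern.** The outcome definition requires 30 days of observation from treatment, but the contact that closes the outcome may come before those 30 days have passed. A woman whose sac was gone on Day 3 has only telephone contacts afterwards, so the final call is the last scheduled check on her status. If she is called early and then has an aspiration or other intervention inside the 30 days, she stays recorded as a success. The length of observation also differs between women for no reason connected with the outcome.

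The same question arises for safety. Section 8.1 runs adverse event follow-up from the last administration, and that clock may start later for a woman who takes a second dose. Infection is a named safety outcome in Section 7.4, so the completeness of that follow-up matters.

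**Working it through.** The plan offers no calculation on this point to reproduce. The check is date arithmetic on its own windows, and it does not touch the sample size.

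**Inputs**, as days after Study Day 1 (Day 1 = 0):

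- Final call: + 25 at the earliest, + 30 nominal, + 36 at the latest (Section 6.5).
- First misoprostol dose: about + 1 in both arms (Section 6.2).
- Day 3 visit, days 3 to 6: + 2 to + 5 (Section 6.3, taking its treatment days as study days).
- Day 8 visit, days 6 to 12: + 5 to + 11 (Section 6.4).

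**Formula:** shortfall = (day of anchor + 30) − day of call. A positive value is the number of days of the period that fall after the call.

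| Period counted from | Anchor | Period ends | Call at + 25 | Call at + 30 | Call at + 36 |
|---|---|---|---|---|---|
| Day 1 | 0 | + 30 | 5 short | 0 | 6 past the end |
| First misoprostol dose | + 1 | + 31 | 6 short | 1 short | 5 past the end |
| Second dose at Day 3 visit | + 2 to + 5 | + 32 to + 35 | 7 to 10 short | 2 to 5 short | 4 to 1 past the end |
| Second dose at Day 8 visit | + 5 to + 11 | + 35 to + 41 | 10 to 16 short | 5 to 11 short | 1 past the end to 5 short |

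**Primary outcome (first two rows).** The range + 25 to + 36 contains 36 − 25 + 1 = 12 permitted call days. Calls fall short on 5 of them (+ 25 to + 29) if the anchor is Day 1, and on 6 (+ 25 to + 30) if it is misoprostol. Observation can differ between women by 36 − 25 = 11 days. If treatment is delayed by d days and Day 1 is not re-dated, the shortfall grows by d. The document does not say whether Day 1 is re-dated.

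**Adverse events.** If study treatment ends with the first misoprostol dose, the second row applies: the period ends at + 31, and calls up to + 30 are still 1 to 6 days early. If a second dose counts, the last two rows apply. Those rows do not bear on the primary outcome, because a woman who took a second dose is already a failure.

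**Effect on the success rates.** The documents give no rate of late interventions, so this is an assumption. Let L be the share of women in an arm whose first intervention falls after their call but inside the 30 days.

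- Recorded success rate = true rate + L. For L from 0 to 3%, each arm is overstated by 0 to 3 percentage points.
- Recorded difference = true difference + (L in the combined arm − L in the misoprostol arm). With equal L the difference is unchanged.

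**The case against.** The case for leaving the text alone has several parts.

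**The anchor.** Section 7.2 does not name misoprostol. Section 6.2 lists treatment under the Day 1 visit, and Section 6.3 counts in treatment days as if they were study days. Counted from Day 1, a nominal call covers exactly 30 days. This stands, and the one-day shortfall at + 30 is therefore conditional. It does not rescue a call at + 25.

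**The second dose.** A reader might infer that women given a second dose certainly lose up to 16 days of safety follow-up. The documents do not establish this. Section 5.2 describes a single misoprostol administration with or without mifepristone, the Study Summary gives the duration of administration as 24 hours, and Section 3.2 treats anything beyond one dose as an additional intervention. A second dose may therefore not be study treatment at all. The figures in the last two rows hold only if it is.

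**Other routes for safety data.** Section 8.1 has women told to report later events thought to be related, and has unresolved events followed up. Section 9 covers possibly related serious events after the study period. Section 6.4 adds weekly visits for women managed expectantly after a persistent sac on Day 8. These routes are real, but partly passive and limited in scope. None is designed to catch a late intervention in a woman already counted as a success.

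**The women affected.** Only a woman with an absent sac on Day 3 and no intervention by at least Day 1 + 25 can be misclassified. The uncovered days, 6 of 30, are a share of the calendar, and should not be read as 20% of the risk. This also stands.

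**Conclusion.** The timing conflict is real. Under either reading of treatment, a permitted call can close the primary outcome before its window ends: by 5 or 6 days at + 25, and by 0 or 1 day at + 30. Late interventions in women counted as successes can be missed, and observation time varies by up to 11 days. The size of the effect is unknown and probably small.

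Because treatment is open-label, a reader might infer that the comparison between arms is biased. The documents do not support that. Both arms take misoprostol at about the same time and share the same call range, and nothing suggests that call timing or late interventions differ by arm.

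The safety part is conditional. If a second dose is study treatment, its 30-day period ends at Day 1 + 32 to + 35 (Day 3 visit) or + 35 to + 41 (Day 8 visit). The latter can fall up to 5 days after the last permitted call, with only partly passive reporting from then on.

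All figures assume misoprostol at Day 1 + 1 and no further treatment delay. The point is worth correcting because the plan as written conflicts with its own definition and the correction is cheap.

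**What to change.** - Reconcile Sections 3.1, 6.5, 7.2 and 8.1 on one stated anchor, and align the references to study day 30 in Sections 4.4.2 and 6.4. State whether Day 1 is re-dated when treatment is delayed.
- Open the final call window only after the 30-day outcome window has closed. If the anchor is misoprostol, that is at least 31 days after Day 1.
- Count interventions for the primary outcome to one common cut-off of 30 days from the anchor, whatever the date of the call, and record the date of each intervention.
- State whether a second misoprostol dose is study treatment for Section 8.1. If it is, time the last adverse event contact to cover 30 days from that dose.

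The cost is protocol wording, slightly later calls for most women, and one later or repeat call for some women who take a second dose. The sample size does not change.

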6.6 Additional Visits

- If an extrauterine pregnancy is diagnosed at any point during the study, appropriate management (medical or surgical) will be instituted within the standard of care and after a full discussion of appropriate options with the subject.
- Contraceptive counseling will be initiated at the study day 1 visit and performed throughout the study. If the participant desires a method of contraception, she will be instructed to begin its use after the study is completed.
- If the subject does not return for any visit, she will be telephoned to reschedule the visit. All efforts will be made to maintain confidentiality if telephone calls are necessary. If the subject is unable to be reached by phone within one week of her scheduled visit, a certified letter must be sent indicating her need to return.

7 Statistical Plan

7.1. Sample Size Determination

Sample size calculations are based on detecting differences in the success rates between the misoprostol only and combined groups. Based upon prior research, we would expect a 60-71% single-dose success rate in the misoprostol only group [25]. Our preliminary data showed a 90% single-dose

success rate in the combined group using the proposed study regimen [11]. If we assume a conservative 85% success rate estimate for combined (C) and 70% success in the misoprostol only (M), we require 134 participants/group to show a difference if one is there (Table 2). To arrive at the total number of women needed to enroll, we inflate this estimate by 10% for loss to follow-up (5%) and interim analysis (5%). We will have adequate power to show a difference in success rates for all proportions above 10%. Thus, our proposed recruitment goal of 300 women (150/group) will enable us to find a clinically meaningful difference of 15% and confidently find the expected difference (20%) between groups.

Combination success rate	Misoprostol only success rate				
	50%	60%	65%	70%	75%
80%	n = 45 C: ±11.7% M: ±14.6%	n = 91 C: ±8.2% M: ±10.1%	n=151 C: ±6.4% M: ±7.6%	n = 313 C: ±4.4% M: ±5.1%	n = 1134 C: ±2.2% M: ±1.7%
85%	n = 33 C: ±12.2% M: ±17.1%	n = 57 C: ±9.3% M: ±12.7%	n=83 C: ±7.7% M: ±10.3%	n = 134 C: ±6.8% M: ±7.8%	n = 270 C: ±4.2% M: ±5.1%
90%	n = 25 C: ±11.8% M: ±19.6%	n = 38 C: ±9.5% M: ±15.6%	n=51 C: ±8.2% M: 13.1%	n = 72 C: ±6.9% M: ±10.6%	n = 113 C: ±5.5% M: ±8.0%
95%	n = 18 C: ±10.3% M: ±23.8%	n = 26 C: ±8.4% M: ±19.2%	n = 31 C: ±7.7% M: ±17.0%	n = 42 C: ±6.5% M: ±14.0%	n = 55 C: ±5.8% M: ±11.5%

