7.4. Interim Analysis

Since safety and failure is a consideration in this study, we have chosen to use a group sequential design. Thus, in addition to the final analysis, we are planning on performing an interim statistical analysis during the course of the study. The purpose of the interim analyses will be to determine whether or not there is sufficient evidence of an increased failure rate in the combined arm compared to the control such that the trial should be discontinued prior to reaching the target accrual goal. The interim analysis will be performed after approximately 1/2 (150 subjects) of the total required patients have completed their primary outcome. This interim analysis will also examine whether or not there is sufficient evidence of an increased infection rate in the combined arm.

The primary outcome for the interim analyses will be the comparison of success/failure rates between the treatment arms. This comparison will be accomplished by means of a simple logistic regression model for the outcomes versus treatment. An approximate O’Brien-Fleming boundary will be used at the interim look to calculate the nominal significance level to which interim p-values are compared (O’Brien PC 1979). Using the O’Brien Fleming spending function, the two analyses (interim + final) should use the following incremental α values (0.003, 0.047) in order to achieve an overall $\alpha=0.05$.

Stopping criteria are for:

(1) **Clear superiority** -- whether the misoprostol alone is clearly inferior to combined treatment. For these calculations, we trade off the power to detect a difference and the size of that difference. Assuming $\alpha=0.003$ for boundaries for the interim analysis when 150 women have been followed to completion power is limited except to detect large reductions in failure rates. For example, power is approximately 0.80 to detect a reduction from 30% in the misoprostol alone arm to 6.7% in the

combination arm. Thus, early or premature stopping for superiority is unlikely, without dramatic improvement from the combined treatment.

(2) **Inferiority.** Power is limited to identify inferiority of the combined treatment, with 0.8 power to demonstrate a 30%-point increase in the risk of failure from 30% in the misoprostol alone arm to 60.7% in the combined treatment arm. Instead, we will base inferiority on the safety concern (see (4)) of an increased failure rate in the combination arm.

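### Section 7.1 claims adequate power for every difference above 10 points, but 150 women per group give 80% power only from about 14 points at the planned 70% control rate

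*Combined protocol and SAP*

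**What the plan says.** Section 7.1 expects a control success rate in this range: "we would expect a 60-71% single-dose success rate in the misoprostol only group". It plans on 70% with misoprostol alone against 85% with the combination. Table 2 gives that cell as "n = 134 C: ±6.8% M: ±7.8". The 134 per group is inflated by 10% (5% for loss to follow-up, 5% for the interim analysis) to 150 per group, 300 in all.

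The section then says: "We will have adequate power to show a difference in success rates for all proportions above 10" per cent. The next sentence is narrower. It names 15% as the clinically meaningful difference and says the trial will "confidently find the expected difference (20%) between groups".

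Table 2 has two cells at exactly 10 points with a control rate of 70% or more: 80% versus 70%, "n = 313 C: ±4.4% M: ±5.1", and 85% versus 75%, "n = 270 C: ±4.2% M: ±5.1".

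Section 7.2 gives the test: "For categorical data, chi-square test will be used". Section 7.4 sets an overall alpha of 0.05 and says the interim and final analyses "should use the following incremental α values (0.003, 0.047"). Section 7.1 itself gives no alpha, sidedness or target power.

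**The concern.** The claim covers every difference above 10 points, yet the section's own table asks for 270 to 313 women per group at 10 points, about twice the 150 enrolled. Required size falls smoothly as the difference grows, so a gap that large at 10 points cannot close just above it.

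The stake is how a non-significant result would be read. Section 7.1 is where a reader learns which benefits the trial could have detected. Taken at its word, the sentence would let a null result count as good evidence against a benefit of 11 to 13 points, when the design would often miss one.

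**Working it through.** **Inputs.** From Section 7.1: 70% versus 85%, control range 60–71%, 134 per group before inflation, 150 per group enrolled, 5% loss. From Section 7.2: chi-square test. From Section 7.4: overall alpha 0.05, final level 0.047. Inferred: two-sided testing and 80% power.

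**Reproducing Table 2.** With p̄ the mean of the two rates and d their difference,

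m = [1.96·√(2p̄(1−p̄)) + 0.8416·√(p₁(1−p₁)+p₂(1−p₂))]² / d²

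n with continuity correction = (m/4)·[1 + √(1 + 4/(m·d))]²

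For 70% versus 85%, m = (1.1575 + 0.4889)²/0.15² = 120.5, and the corrected n is 133.5, so 134 as printed. Variants that do not give 134: uncorrected 121, 90% power uncorrected 161, one-sided uncorrected 95. The corrected formula returns all 15 cells in the 80%, 85% and 90% rows exactly, including 313, 270 and 151. In the 95% row three cells are within 1, and two are further off (34 against 31, and 59 against 55).

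**Size needed from a 70% control rate (80% power).**

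| Difference | n per group, uncorrected | n per group, corrected |
|---|---|---|
| 10 points | 294 | 313 |
| 11 points | 239 | 257 |
| 12 points | 198 | 214 |
| 13 points | 166 | 181 |
| 14 points | 141 | 155 |

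**Power at 150 per group.** Power = Φ{[d − 1.96·√(2p̄(1−p̄)/n)] / √((p₁(1−p₁)+p₂(1−p₂))/n)}. For the corrected version, d is reduced by 1/n.

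Example, 70% versus 81%: the two standard errors are √(2·0.755·0.245/150) = 0.04966 and √((0.21 + 0.1539)/150) = 0.04925. Uncorrected, (0.11 − 1.96·0.04966)/0.04925 = 0.257, so power is 60.1%. Corrected, with d = 0.11 − 0.00667, it is 54.8%.

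| Difference | Control 70%: uncorrected (corrected) | Control 60%: uncorrected (corrected) |
|---|---|---|
| 10 points | 51.6% (46.3%) | 44.2% (39.5%) |
| 11 points | 60.1% (54.8%) | 51.8% (46.9%) |
| 12 points | 68.4% (63.4%) | 59.3% (54.5%) |
| 13 points | 75.9% (71.4%) | 66.6% (62.0%) |
| 14 points | 82.5% (78.7%) | 73.4% (69.2%) |
| 15 points | 87.9% (84.8%) | 79.5% (75.8%) |

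Exact binomial enumeration of the chi-square test at 70% control agrees: 60.5%, 68.8% and 76.4% at 11, 12 and 13 points (corrected 55.2%, 63.8% and 72.0%).

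**Smallest difference with 80% power, uncorrected (corrected).**

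| n per group | Control 70% | Control 60% |
|---|---|---|
| 150 | 13.6 (14.2) points | 15.1 (15.7) points |
| 142, i.e. 150 × 0.95 = 142.5 rounded down | 13.9 (14.6) points | 15.5 (16.1) points |

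**Other checks at 142 per group.** 70% versus 85%: 86.1% (82.6%). Ten points: 42.3% (37.5%) from 60% and 49.4% (44.0%) from 70%. Twenty points, control 60–70%: 96.1–99.0% (94.8–98.5%). At a final level of 0.047, 70% versus 85% becomes 85.5% (81.9%), and the 10-point powers also fall by about 1 point.

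**The case against.** The strongest reply is that the sentence does no work. The next one states the real target, 15 points, and the expected 20, and both are adequately powered at the planned 70% control rate. Table 2 openly shows that 10 points needs far more women. On the plan's own rates the smallest difference foreseen is 71% versus 85%, 14 points, where power at 150 per group is 83.7% (79.9% corrected). Differences of 11 to 13 points require a combination rate below the plan's conservative 85%. This stands as a limit on the consequence: the trial was not sized for those effects and its size is not in doubt. It does not make the sentence true, and the narrower sentence after it does not withdraw it.

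A second reply is that the benchmark is inferred and the wording loose. Both are fair. One-sided 0.05 without correction would give 72%, 79% and 85% at 11, 12 and 13 points, but it does not reproduce the table, and two of those three are still below 80%. If the 10% referred to success rates themselves, the claim would cover every cell of Table 2, including the one needing 1134 per group, and would be less tenable still. Ten points would have about 83% power at a control rate near 85%, but that is well outside the expected 60–71%.

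**Conclusion.** The concern holds. At 150 per group and a 70% control rate, power for 11 to 13 points is 60–76% uncorrected, or 55–71% by the method behind Table 2. A true benefit of that size would be missed about 24–40% of the time (29–45% corrected). The claim fails from 10 up to about 13 points at a 70% control rate, and up to about 15 points at 60%.

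This rests on reading the claim as a percentage-point difference, on two-sided 0.05, and on 80% as adequate power. The last two are inferred, but together with the continuity correction they return the planned 134 exactly. The error lies in the stated sensitivity. The 70% versus 85% calculation, the recruitment goal and the 20-point statement are sound, and no analysis or stopping rule depends on the sentence. It should be corrected, but the design need not change.

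**What to change.** Keep 300 women and replace the sentence with text such as:

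> With a two-sided chi-square test at 0.05 and 142 evaluable women per group (150 less 5% loss), power for 70% versus 85% is about 86% (83% with the continuity correction used for Table 2). The smallest difference with 80% power is about 14 points at a 70% control rate and 15.5 points at 60% (14.6 and 16.1 with the correction). Power for a 10-point difference is about 42–49% (38–44% with the correction) for control rates of 60–70%.

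The authors should confirm the two-sided level and the 80% target and state them in Section 7.1. If 0.047 is the final level, add that these powers fall by about 1 point. A shorter alternative is to delete the sentence and give only the 14-point figure with its control rate. The 20-point statement may stay.

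Two side matters, neither affecting the sample size:

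- Ask the authors whether the 20% reduction in failures in the Section 2 hypothesis is in percentage points or relative, and whether it is the expected effect rather than a tested threshold.
- Recompute Table 2 from one formula. For example, the 85%/70% cell prints ±6.8% for the combination, where 1.96·√(0.85·0.15/134) gives ±6.0%. The 80%/75% cell prints ±1.7% for misoprostol alone, where n = 1134 gives ±2.5%. The sizes 31 and 55 in the 95% row should be 34 and 59 when rounded up.

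The cost is wording only. The stated power for small differences becomes less favourable. No patients are added, and neither the design nor the analysis changes.
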